### **Endometrial Biopsy**

Instructions on endometrial biopsy collection and processing procedures for shipping will be provided by the central laboratory. Sites can use the endometrial biopsy instruments provided by the Central Lab or any other endometrial biopsy instruments available at the study site. Subjects must have a confirmed negative urine pregnancy test within 24 hours prior to undergoing the endometrial biopsy.

Pre-medication for the endometrial biopsy procedure is allowable and should be recorded in source documents and on the appropriate eCRF. Misoprostol for cervical dilatation is allowable. An office hysteroscopy may be performed to obtain the endometrial biopsy sample if the endometrial biopsy cannot be performed because of anatomical reasons.

An endometrial biopsy will be performed at the Treatment Period Month 6 Visit or at the Premature Discontinuation Visit (if the subject prematurely discontinues after the Month 3 Visit).

If the endometrial biopsy is performed on the same day as the Pap smear or pelvic ultrasound, the endometrial biopsy should be performed after the Pap smear and pelvic ultrasound.

In the event that the Month 6 or Premature Discontinuation Visit endometrial biopsy cannot be performed (e.g., due to a stenotic cervix or location of fibroids), or an insufficient biopsy sample is obtained and the concurrent TVU indicates a thickness of > 4 mm, a repeat biopsy must be performed. If upon repeat, a sample cannot be obtained or remains insufficient, the AbbVie TA MD should be consulted.

Subjects with abnormal endometrial pathology results at Treatment Month 6 will enter the Post-Treatment Follow-Up Period and should be managed according to standard of care. The subject's management plan for any of these significant pathologic findings should be reviewed with the AbbVie TA MD, and the subject outcome documented in the eCRF.

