### **5.4 Removal of Subjects from Therapy or Assessment**

Each subject has the right to withdraw from the study at any time. In addition, the Investigator may discontinue a subject from the study at any time if the Investigator considers it necessary for any reason, including the occurrence of an adverse event or noncompliance with the protocol. Subjects who withdraw from the study will not be replaced. Each subject will be withdrawn from the study if any of the following occur:

- The subject decides to withdraw consent for any reason.
- The investigator believes it is in the best interest of the subject.
- Clinically significant deterioration of the subject's medical status as determined by the investigator.
- The subject requires surgical intervention for treatment of uterine fibroids and menstrual bleeding or other procedures including hysterectomy, myomectomy, uterine artery embolization, high intensity focused ultrasound (HIFU), endometrial ablation, dilation and curettage (D&C), etc. during the Treatment Period. In the post treatment period these procedures do not warrant withdrawal if performed during the Post-Treatment Period unless a hysterectomy with bilateral salpingo-oophorectomy (BSO) is performed and the Subject does not plan to use Hormone Replacement Therapy within 1 month of the surgery date.
- The subject becomes pregnant.

- The subject has ALT or AST elevation > 5 times the upper limit of normal confirmed upon repeat during the Treatment Period.
- The subject's legally acceptable representative decides to withdraw consent for any reason (when applicable).
- Heavy menstrual bleeding during the Treatment Period that requires a blood transfusion at any time after having taken 28 days of study drug. If a subject has a blood transfusion during the Post-Treatment Period, the AbbVie TA MD should be contacted to determine if the subject can remain in the study.
- Any other medical reason that AbbVie or the study investigator deems appropriate.

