7.4 Definition of Analysis Window

7.4.1 Treatment Period

Data obtained more than 3 days after the subject's last dose of study drug in the extension study will be excluded for assessments in the Treatment Period with the following exceptions:

- 1. For BMD, TVU/TAU, MRI, and endometrial biopsy assessments, data obtained more than 28 days after the last dose of study drug in the extension study will be excluded from summaries/analyses in the Treatment Period.
- 2. For Alkaline Hematin (AH) data, data obtained after the last dose of study drug in the extension study will be excluded from the summaries/analyses in the Treatment Period.

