12.2.1 Analysis of Adverse Events in the Extension Study

Adverse events (AEs) in the extenstion study will be summarized using system organ classes (SOCs) and preferred terms (PTs) from the Medical Dictionary for Regulatory Activities (MedDRA) Version 19.0 or higher by the six analysis groups as described in Section 5.3.

For each AE summary, the number and percentage of subjects experiencing at least one AE will be presented. Subjects reporting more than one AE within a SOC will be counted only once for that SOC. Subjects reporting more than one AE for a PT will be counted only once for that PT.

Treatment-emergent AEs are defined as AEs with a start date on or after the first dose of study drug in the extension study. AEs starting more than 30 days following discontinuation of study drug will not be included in summaries of treatment-emergent

COBVIE Elagolix (ABT-620) M12.816 - Statistics

Elagolix (ABT-620) M12-816 – Statistical Analysis Plan Version 2.0 – 24 May 2018

AEs. Post-Treatment AEs are defined as AEs starting more than 30 days following discontinuation of study drug in the Treatment Period of this study.

When summarizing AEs by relationship or severity, if a subject has an event with unknown severity or relationship then the subject will be counted in the severity/relationship category of "unknown" even if the subject has a second occurrence of the same event with a severity/relationship present. The only exception is if the subject has a second occurrence of the same event with the most extreme severity (i.e., "severe") or the most extreme relationship category (i.e., "reasonable possibility"). In this case, the subject will be counted under these most extreme severity/relationship categories.

Treatment Period

The number and percentage of subjects with treatment-emergent AEs will be calculated by analysis group as follows:

- Any AEs
- Any AEs by primary MedDRA system organ class (SOC) and preferred term (PT)
- Any AEs occurring in ≥ 5% of subjects by primary MedDRA system organ class (SOC) and preferred term (PT)
- Any AEs by PT in descending frequency of 12 month elagolix 300 mg BID plus E2/NETA treatment group
- Any AEs by maximum severity (by primary MedDRA SOC and PT)
- Any AEs by maximum relationship (by primary MedDRA SOC and PT)
- Any AEs reasonably possibly related to study drug (by primary MedDRA SOC and PT, by PT)
- Any AEs leading to study drug discontinuation (by primary MedDRA SOC and PT)

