• Change in liver enzymes (SGPT/ALT, SGOT/AST, total bilirubin, and alkaline phosphatase) and lipid parameters (LDL-C, HDL-C, TG, and total cholesterol) from Baseline to relevant Post-Treatment Follow-up visit(s) will be summarized by the four main analysis groups as in Section 5.3 with descriptive statistics.

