12.3.2 Assessment of Hepatotoxicity

The number and percentage of subjects in each analysis group with maximum on-treatment laboratory values meeting the following criteria compared to the upper limit of normal (ULN) will be summarized by the six analysis groups as in Section 5.3 to assess potential hepatotoxicity.

- ALT \geq 3 × ULN and total bilirubin \geq 2 × ULN
- AST \geq 3 × ULN and total bilirubin \geq 2 × ULN
- ALT and AST \ge 3 × ULN and total bilirubin \ge 2 × ULN
- ALT \ge 3 × ULN and total bilirubin < 2 × ULN
- AST \geq 3 × ULN and total bilirubin < 2 × ULN
- ALT and AST \geq 3 × ULN and total bilirubin < 2 × ULN
- ALT \ge 3 × ULN and total bilirubin \ge 1.5 × ULN
- AST \geq 3 × ULN and total bilirubin \geq 1.5 × ULN
- ALT and AST \ge 3 × ULN and total bilirubin \ge 1.5 × ULN
- $ALT \ge 3 \times ULN, \ge 5 \times ULN, \ge 10 \times ULN, \ge 20 \times ULN$
- $AST \ge 3 \times ULN, \ge 5 \times ULN, \ge 10 \times ULN, \ge 20 \times ULN$
- Total bilirubin $\geq 1.5 \times ULN$, $\geq 2.0 \times ULN$.

The maximum ratio relative to the ULN is used to determine if subjects met the criteria listed above. The ALT, AST, and total bilirubin values do not need to be concurrent in order to meet the defined criteria. For ALT, AST, and total bilirubin, a subject is counted

if the post-baseline laboratory value during the Treatment Period meets the above criteria regardless of Baseline laboratory value (i.e., the post-baseline laboratory value does not need to be worse than Baseline laboratory value).

A listing of all ALT, AST, total bilirubin, and alkaline phosphatase values will be provided for each subject who met any of the criteria defined above.

The following eDISH plots will be generated: peak ASL vs. peak bilirubin; peak ALT vs. peak bilirubin.

12.4 **Bone Mineral Density**

All analyses and summaries of bone mineral density (BMD) will be performed for each segment, i.e., femoral neck, lumbar spine, and total hip. For subjects who had a right-side scan performed (rare instances), their data for right femoral neck and right femoral total hip were included in the analysis with the data for the left femoral neck and left total hip, respectively (available for the majority of subjects), and an additional analysis was performed using the left side only. If more than one scan is reported for an anatomical segment within an analysis window, the worse (the lower value) of the multiple measurements were used for analysis for each anatomical segment.

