12.6 Endometrial Biopsy

The number and percentage of subjects in each category of endometrial biopsy results will be summarized at Baseline, Prior to Month 6, and Month 6 for each of the six analysis groups as in Section 5.3. If multiple assessments exist in a specific time window, all assessments will be displayed.

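### A liver threshold first crossed more than 3 days after the last dose is missed by the hepatotoxicity counts and listing, and a biopsy more than 28 days after it has no planned summary

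*SAP*

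**What the plan says.** **Liver.** SAP 7.4.1 limits Treatment Period laboratory data: "Data obtained more than 3 days after the subject's last dose of study drug in the extension study will be excluded for assessments". SAP 12.3.2 then counts women by their maximum on-treatment ALT, AST and bilirubin as multiples of ULN. A woman qualifies "if the post-baseline laboratory value during the Treatment Period meets the above criteria". The accompanying listing gives all liver values for each woman who met a criterion.

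Later values move to follow-up under SAP 7.4.2 and 12.3.1. There, all laboratory variables get group statistics including a minimum and maximum, and the plan adds "Change in liver enzymes (SGPT/ALT, SGOT/AST, total bilirubin, and alkaline phosphatase" among the changes from baseline summarised by visit. The follow-up shift tables, by normal range and by CTCAE grade, cover lipids only. The eDISH plots use peak values, with no period stated.

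The adverse-event window is longer: "AEs starting more than 30 days following discontinuation of study drug will not be included in summaries of treatment-emergent" events (SAP 12.2.1).

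**Biopsy.** SAP 7.4.1 has a separate limit: "For BMD, TVU/TAU, MRI, and endometrial biopsy assessments, data obtained more than 28 days after the last dose of study drug" are excluded from the Treatment Period. The matching 28-day exception in SAP 7.4.2 names BMD, ultrasound and MRI but not biopsy. SAP 12.6 has results "summarized at Baseline, Prior to Month 6, and Month 6". Where the end-of-treatment sample cannot be obtained or is insufficient and the endometrium is thicker than 4 mm, Protocol 5.3.1.1 says "a repeat biopsy must be performed". It gives no deadline.

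**The concern.** A hepatotoxicity screen by ULN multiple looks for individual women, and for ALT and bilirubin rises in the same woman. Group means and maxima do not do that. If the screen closes at day 3, a woman whose first qualifying value is drawn at a late exit visit, at an unscheduled recheck or at the first follow-up visit is outside it. Those most exposed are women who stop early. Protocol 5.4.1 asks for their exit visit as soon as possible and preferably within 2 days of the last dose, but sets no upper limit.

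For the endometrium, the study design lists endometrial health as an aim, SAP Appendix M names biopsy results as a surveillance method, and Protocol 3.2.2 reports one endometrial adenocarcinoma in the Phase 2b elagolix-alone arm. A repeat taken because the first sample failed can be the only informative tissue result for that woman. If it comes late, no planned biopsy output shows it.

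**Working it through.** The plan states no figure here to reproduce. The check traces each value through the windows.

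**Liver**

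Inputs: 3-day cut-off (SAP 7.4.1); 30-day adverse-event window (SAP 12.2.1); follow-up Month 1 at day 28 ± 7 (Protocol Table 1) with chemistry drawn (Protocol Appendix C); Table 4 window for Post-Treatment Month 1; choice of the value nearest the nominal day (SAP 7.4.4).

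1. Mismatch: 30 − 3 = 27 days. On days 4 to 30 after the last dose an adverse event is treatment-emergent, but a liver value cannot enter the 12.3.2 counts.
2. Follow-up Month 1 visit: 28 − 7 = 21 to 28 + 7 = 35. All of these samples lie outside 12.3.2. Days 21 to 30, which are 10 of the 15 permitted days, lie inside the adverse-event window.
3. Destination: Table 4 as printed assigns days 4 to 41 to Post-Treatment Month 1. Take a recheck on day 10 and a visit on day 28. The distances from nominal are |10 − 28| = 18 and |28 − 28| = 0, so the day-28 value is used. A day-10 peak drops out of the by-visit summary.
4. Reading 12.3.2 literally gives three cases:

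| Case | Counts | Hepatotoxicity listing |
|---|---|---|
| All crossings by day 3 | Counted in full | All her values |
| ALT ≥ 3 × ULN by day 3, bilirubin first ≥ 2 × ULN later | Counted with bilirubin below 2 × ULN | All her values, no date limit printed |
| No criterion met by day 3, first met later | Not counted | Not listed |

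**Biopsy**

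Inputs: Month 6 visit at Day 168, −4 or +6 days, with dosing until the visit (Protocol 5.1, Visit Windows); 28-day limit (SAP 7.4.1); Table 3 Month 6 window, above Day 140 up to Day 196.

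| Last dose | 28-day limit | Days past Table 3 |
|---|---|---|
| Day 164 | 164 + 28 = 192 | 0 |
| Day 168 | 168 + 28 = 196 | 0 |
| Day 174 | 174 + 28 = 202 | 202 − 196 = 6 (Days 197 to 202) |

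For an early stopper with last dose on Day 100, a biopsy on Day 128 is kept in the Prior to Month 6 row. One on Day 129 is excluded by the 28-day rule, although Table 3's range for that row runs to Day 140.

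After day 28, the general rule in SAP 7.4.2 nominally admits a biopsy to follow-up. But Tables 4 to 7 do not name biopsy among their examples, and SAP 12.6 has no follow-up row.

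**The case against.** The strongest reply is that these values are reassigned and not discarded. A reader might infer that late liver values disappear from reporting, or that mandated repeat biopsies are lost. The documents do not support either reading:

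- Late liver values enter the follow-up descriptive summaries, which include a maximum. Month 1 follow-up samples have a Table 4 window.
- A woman who met a criterion on treatment has all her liver values listed. The protocol's withdrawal criterion is "ALT or AST elevation > 5 times the upper limit of normal confirmed upon repeat during the Treatment Period", so a woman stopped under it had already passed 3 × ULN and is listed.
- The eDISH plots carry no written restriction to the Treatment Period.
- Protocol 8.1.8.3 flags high values in data listings without limiting the period.
- Repeat biopsies within 28 days and inside a window are kept, and SAP 12.6 displays all of them. If a central read took one to two weeks (assumed) after a biopsy on the last dosing day, 28 − 14 = 14 to 28 − 7 = 21 days would remain for a repeat.
- Serious findings can surface as adverse events, including those starting after day 30. Endometrial safety is an item of special interest.
- With an elagolix half-life of 4 to 6 hours (Protocol 3.2.2), 3 days is 72/6 = 12 to 72/4 = 18 half-lives.

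Most of this stands, and it limits the point. It does not close the gap for a first crossing after day 3. The follow-up maximum is a group statistic, is not scaled to ULN and does not pair ALT with bilirubin. Under Protocol 6.1.1.1 a laboratory abnormality is an adverse event only if it leads to discontinuation from the study, needs intervention or is judged one by the investigator, and Appendix M has no hepatic search. Drug clearance supports an on-treatment table but does not show that a liver signal must appear within 3 days. The SAP itself allows 30 days for adverse events and hospitalisations and 28 for biopsy.

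**Conclusion.** The point holds as two narrow reporting gaps that should be closed. First, a woman with no qualifying liver value by day 3 who first crosses an ALT, AST or bilirubin threshold afterwards is absent from the SAP 12.3.2 counts and listing, and follow-up has no ULN-multiple or CTCAE liver table. Second, biopsies more than 28 days after the last dose have no planned summary, and up to 6 days of biopsies within the 28-day rule have no window when the last dose falls on Day 174.

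The size can be stated only as time: 27 days of mismatch for liver values and 6 days for the Table 3 gap. The documents give no rate of late liver crossings, late exit visits or repeat biopsies, so a number of women would be guesswork. The finding assumes that on-treatment in SAP 12.3.2 means the Treatment Period of SAP 7.4.1, and that the SAP 7.4.4 selection rule applies to follow-up chemistry.

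**What to change.** **Liver (SAP 12.3.2)**
- Keep the on-treatment table.
- Add a supplementary table and listing with the same ALT, AST and bilirubin categories, using all values from first dose through 30 days after the last dose, scheduled or not.
- State the period that the eDISH plots cover.

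**Biopsy (SAP 7.4.2, Table 3, 12.6)**
- Add endometrial biopsy to the 28-day exception in SAP 7.4.2.
- Close the gap between Day 196 and the 28-day limit, so that every biopsy admitted by SAP 7.4.1 has a window.
- Add to SAP 12.6 a post-treatment row or listing of all later biopsy results, including mandated repeats, flagged by days since last dose. Do not substitute them for the Month 6 result.

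The cost is SAP wording, one supplementary table and listings, all on data already collected. No study procedure changes. The downside is that a few liver values unrelated to drug may enter the 30-day table. Keeping the on-treatment table beside it lets the reader see which they are.

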### **5.4.3 Treatment Interruption**

AbbVie or the Investigator may request that a subject temporarily discontinue study drug administration, which will be referred to as "treatment interruption." The following are examples for reasons when the AbbVie TA MD must be notified in order to assess whether a subject should undergo temporary treatment interruption:

- Adverse event, that based on clinical judgment, requires temporary suspension of treatment or prevents a subject from taking study drug
- Due to malfunction of barrier contraception or unprotected intercourse

Additionally, there may be times when a subject has had treatment interruption due to having forgotten to take study drug, lost study drug, etc. If the subject has missed 7 or more consecutive days of dosing (with either ABT-620 or elagolix plus E2/NETA), the AbbVie TA MD must be consulted to determine whether the subject may resume study drug administration or continue in the Treatment Period.

These examples are not all-inclusive; if the Investigator has any questions, these should be directed to the AbbVie TA MD.

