7.4.2 Post-Treatment Follow-Up Period

Summaries for the Post-Treatment Follow-up Period will include data obtained more than 3 days after the subject's last dose of study drug with the following exceptions:

- For BMD, TVU/TAU, and MRI assessments, data obtained more than 28 days after the last dose of study drug in the extension study will be included in the summaries during the Post-Treatment Follow-up Period.
- For AH data, data obtained after the last dose of study drug in the extension study will be included in the summaries during the Post-Treatment Follow-up Period.

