7.4.3 Details Regarding Visit Windows

For analyses in the Treatment Period in the extension study, time points and corresponding time windows are defined based on the time of exposure to study drug starting from Study Day 1 in the extension study.

The time windows described in this section will not be applied to bleeding assessments including AH data and Uterine Bleeding Questionnaire (UBQ). Rules described in Section 7.4.1 and Section 7.4.2 will be applied prior to defining time windows. Data considered as in the Treatment Period are not considered in the Post-Treatment Follow-up Period as described in Section 7.4.1 and Section 7.4.2. Any data considered as Baseline (see Section 7.1) will not be included in any post-baseline windows.

Table 1 will be used for analyses of endpoints collected monthly in the Treatment Period of the extension study.

Visit	Nominal Day (Study Day)	Time Window (Study Days)
Month 1	28	$> 1 - \leq 42$
Month 2	56	$> 42 - \le 70$
Month 3	84	$> 70 - \le 98$
Month 4	112	$> 98 - \le 126$
Month 5	140	$> 126 - \le 154$
Month 6	168	$> 154 - \le 196$

Table 1.Analysis Time Windows for Non-Bleeding Measurements Collected
Monthly

Table 2 will be used for analyses of endpoints collected every 3 months in the Treatment Period of the extension study. If there is a scheduled Month 1 visit for the endpoint (e.g., PGIC-MB and PGIC-NBUFS), the first subtable will be used. If there is no scheduled Month 1 visit for the endpoint (e.g., TAU/TVU, BMD, urinalysis, apolipoprotein A and B, reflexive TSH, thyroxine-binding globulin (TBG), UFS-QoL), the second subtable will be used.

Table 2.Analysis Time Windows for Non-Bleeding Measurements Collected
Every 3 Months in the Treatment Period

Visit	Nominal Day (Study Day)	Time Window (Study Days)
Month 1	28	> 1 - ≤ 56
Month 3	84	$> 56 - \le 140$
Month 6	168	$> 140 - \le 196$
Visit	Nominal Day (Study Day)	Time Window (Study Days)
Prior to Month 3	28	$> 1 - \le 56$
Month 3	84	$> 56 - \le 140$
Month 6	168	$> 140 - \le 196$

Table 3 will be used for analyses of endpoints collected at Month 6 (biopsy, MRI, creatinine phosphokinase, EQ-5D-5L, WPAI) in the Treatment Period of the extension study.

Table 3.Analysis Time Windows for Non-Bleeding Measurements Collected
Every 6 Months in the Treatment Period

Visit	Nominal Day (Study Day)	Time Window (Study Days)
Prior to Month 6	70	$> 1 - \le 140$
Month 6	168	$> 140 - \le 196$

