11.3.6.6 Number of Days in Hospital

Hospitalization related data will be summarized as observed; missing data will not be imputed. Hospitalization data will be summarized by analysis group in the Treatment Period based on the Adverse Events eCRF.

The number and percentage of subjects who were hospitalized or had prolonged hospitalization will be summarized by analysis group. If a subject was hospitalized or had prolonged hospitalization multiple times during the Treatment Period, she will be counted only once.

The number of hospitalizations will be summarized by analysis group. The number of days in hospital (i.e., discharge date - admission date + 1) will be summarized by analysis

group. Only hospitalizations with an admission date on or after the first dose date and within 30 days following the last dose date (i.e., first dose date \leq admission date \leq last dose date +30) are included in the analysis of the number of days in hospital. If discharge date or admission date is missing, then the hospitalization will be excluded from the analysis of the number of days in hospital.

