- LDL-C/HDL-C ratio: ≤ 3 , and > 3
- Total cholesterol/HDL-C ratio: ≤ 4.5 , and > 4.5.

In addition, the number and percentage of subjects who have potentially clinically significant (PCS) lipid values meeting the following criteria any time during the Treatment Period will be summarized by the six analysis groups as in Section 5.3:

- Total cholesterol > 200 mg/dL
- LDL-C > 130 mg/dL
- LDL-C > 160 mg/dL
- HDL-C < 40 mg/dL
- TG > 150 mg/dL
- TG/HDL-C ratio > 3.5
- LDL-C/HDL-C ratio > 4.

Plots will be provided by the four main analysis groups as in Section 5.3 for HDL-C, LDL-C, triglycerides, and hemoglobin during the Treatment Period:

- Final post-baseline lab values vs. Baseline lab values;
- Final post-baseline lab values vs. Baseline lab values for subjects with NCI CTCAE Grade 3 or 4;
- Maximum post-baseline lab values vs. Baseline lab values;
- Maximum post-baseline lab values vs. Baseline lab values for subjects with NCI CTCAE Grade 3 or 4.

Plots will be provided by the four main analysis groups as in Section 5.3 for HDL-C, LDL-C, and triglycerides during the Treatment Period:

• Mean percent change from Baseline in lipid over month.

Post-Treatment Follow-Up Period

All laboratory variables will be summarized with mean, median, standard deviation, minimum, and maximum by the four main analysis groups as in Section 5.3.

Laboratory data collected more than 3 days after the last dose of study drug in the Treatment Period will be included in the summary of data from the Post-Treatment Follow-up Period. Baseline for summaries/analyses in the Post-Treatment Follow-up Period is the same as Baseline for summaries/analyses in the Treatment Period.

In the Post-Treatment Follow-up Period, the following summaries will be presented:

- During the Post-Treatment Follow-up Period, shift tables for change from Baseline to relevant Post-Treatment Follow-up visit(s) according to the normal ranges will be provided for LDL-C, HDL-C, TG, and total cholesterol by the six analysis groups as in Section 5.3.
- During the Post-Treatment Follow-up Period, shift tables for change from Baseline to relevant Post-Treatment Follow-up visit(s) will also be presented

based on the CTCAE grades for LDL-C, HDL-C, TG, and total cholesterol by the four main analysis groups as in Section 5.3.

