12.8 Columbia Suicide Severity Rating Scale (C-SSRS)

The C-SSRS data will be summarized as observed by the six analysis groups as in Section 5.3. The C-SSRS – Since Last Visit questionnaires and corresponding scoring rules are presented in Appendix J and Appendix K.

The number of subjects with suicidal ideation, suicidal behavior, and self-injurious behavior without suicidal intent at each scheduled assessment during the Treatment Period (including Day 1) will be summarized.

The number of subjects with suicide-related treatment-emergent events based on the C-SSRS during the Treatment Period (including Day 1) will be summarized.

A listing of subjects with suicidal ideation, suicidal behavior, or self-injurious behavior without suicidal intent based on the C-SSRS during the Treatment Period (including Day 1) will be provided.

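### A C-SSRS form completed at a premature discontinuation visit more than 3 days after the last dose falls outside every C-SSRS output that SAP 12.8 defines

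*SAP*

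**What the plan says.** SAP 7.4.1 gives the default rule for the Treatment Period: "Data obtained more than 3 days after the subject's last dose of study drug in the extension study will be excluded for assessments". It names two exceptions. BMD, ultrasound, MRI and endometrial biopsy data are kept up to 28 days after the last dose, and alkaline hematin data are cut at the last dose. The C-SSRS is in neither.

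SAP 7.4.2 routes later data onward: "Summaries for the Post-Treatment Follow-up Period will include data obtained more than 3 days after the subject's last dose of study drug". SAP 7.4.3 fixes the order of operations: "Rules described in Section 7.4.1 and Section 7.4.2 will be applied prior to defining time windows".

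SAP 12.8 defines three C-SSRS outputs: counts at each scheduled assessment, treatment-emergent suicide-related events, and a listing. Each is restricted to the Treatment Period, with Day 1 included. The listing is worded as "A listing of subjects with suicidal ideation, suicidal behavior, or self-injurious behavior without suicidal intent based on the C-SSRS during the Treatment Period".

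In the protocol, section 5.3.1.1 has the C-SSRS given during the Treatment Period in its since-last-visit form. Section 5.4.1 asks for the Treatment Period Premature Discontinuation Visit as soon as possible. It prefers 2 days or less from the last dose and states no upper limit.

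**The concern.** The C-SSRS is a named safety variable (Protocol 5.3.5), and mood disorders including suicidality are of special interest for this drug (Protocol 3.2.2). The form looks back to the previous visit. If it is completed a few days after stopping, it can describe ideation or behavior that occurred on drug.

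The exposure is uneven. Completers are told to keep dosing until they return for Month 6 (Protocol 5.1, Visit Windows), so their last form stays inside the window. Only women who stop early, including those who stop for adverse events, can lose their last form. What is at stake is the structured C-SSRS result for those women. No efficacy or BMD conclusion is touched, and SAP 12.1 plans no test on the C-SSRS.

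**Working it through.** No figure in the plan needs reproducing; the check is a trace of the rules. Let d be the number of days from the last dose to the C-SSRS form completed at the Premature Discontinuation Visit.

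1. **d of 3 or less.** SAP 7.4.1 keeps the form in the Treatment Period. It is eligible for all three outputs in SAP 12.8.
2. **d greater than 3.** The default rule applies and neither exception names the C-SSRS, so the form is not Treatment Period data. By SAP 7.4.3 this is settled before any visit window is assigned, so a window cannot bring the form back.
3. **Routing.** SAP 7.4.2 makes the form post-treatment data. SAP 12.8 has no post-treatment C-SSRS output, and Protocol 8.1.8.8 adds none. The form enters 0 of 3 outputs.

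Other safety and resource outcomes fare differently:

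| Outcome | Kept after last dose in Treatment Period summaries | Where later data go |
|---|---|---|
| BMD, ultrasound, MRI | 28 days (SAP 7.4.1) | Post-treatment summaries (SAP 7.4.2) |
| Laboratory | 3 days (SAP 7.4.1, repeated in 12.3.1) | Post-treatment summaries (SAP 12.3.1) |
| Adverse events | 30 days (SAP 12.2.1) | Post-treatment AE tables (SAP 12.2.1) |
| Days in hospital | 30 days (SAP 11.3.6.6) | None stated |
| C-SSRS | 3 days by default | None |

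Where a longer window was wanted, it was written into the outcome's own section. For hospital stays: "Only hospitalizations with an admission date on or after the first dose date and within 30 days following the last dose date". For adverse events: "AEs starting more than 30 days following discontinuation of study drug will not be included in summaries of treatment-emergent" events. Laboratory data keep the 3-day cut, but late values are recovered: "Laboratory data collected more than 3 days after the last dose of study drug in the Treatment Period will be included in the summary" of post-treatment data. SAP 12.8 has neither provision.

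**Can d exceed 3 under the protocol?** Yes. The preferred 2 days is only 1 day short of the cut-off (3 − 2 = 1), and it is a preference. Protocol 5.4.3 also lets a woman be held off drug for an adverse event before a decision is made. It covers missed doses too: "If the subject has missed 7 or more consecutive days of dosing", the sponsor's medical director decides whether she may resume. If she is then withdrawn without redosing, d is already at least 7.

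**The case against.** The strongest reply is that Treatment Period in SAP 12.8 means the protocol period. The protocol labels this visit a Treatment Period visit, and 12.8 speaks of scheduled assessments and includes Day 1. A programmer working from visit labels would keep the form. That reading is possible, but the SAP does not state it. Including Day 1 bears only on the start of the period. SAP 7.4.3 refers to 7.4.1 and 7.4.2 for which data belong to which period, and 12.3.1 defines a final Treatment Period laboratory value as one collected within 3 days of the last dose.

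It can also be said that the exceptions in 7.4.1 are not exhaustive, since adverse events and hospital stays have 30 days without being named there. That is true, but each has explicit text and 12.8 has none.

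Three limits stand. The cut-off already exceeds the preferred visit timing. A 7-day gap requires consultation, not withdrawal. And the C-SSRS row of Protocol Appendix C is damaged in the text available; its final X is consistent with the discontinuation column but does not prove it.

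A reader might infer that suicidality in early stoppers would go unreported. The documents do not support that. Protocol 5.3.1.1 requires the investigator to act on ideation and notify the sponsor. Events entered as adverse events within 30 days remain in the tables (SAP 12.2.1) and in the depression and suicide/self-injury search (SAP Appendix M). This cover is partial, because it depends on an adverse event being entered, which Protocol 5.3.1.1 does not expressly require.

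A reader might also try to size the loss by the share of recall days spent on drug, a/(a + d), with a the on-drug days since the previous visit. At d = 4 this is 1/5 = 20% for a = 1 and 28/32 = 88% for a = 28. The result follows the assumed a. It says which days one form covers, not how many forms or events are lost.

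**Conclusion.** The gap is real and worth closing. Under the date rule in SAP 7.4.1, a C-SSRS form from a Premature Discontinuation Visit more than 3 days after the last dose is not Treatment Period data, and SAP 12.8 gives it nowhere else to appear. Its recall can nevertheless include on-drug days.

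The conclusion rests on two assumptions: that the C-SSRS is collected at that visit, and that Treatment Period in 12.8 carries the date-based meaning used elsewhere in the SAP. If the second is wrong, what remains is an ambiguity that one sentence would settle.

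The size is unknown. The documents give no discontinuation rate, no distribution of visit delays and no rate of positive forms. It is probably small: at most the last treatment-period form of some women who stop early.

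**What to change.** 1. Extend the SAP 12.8 listing to every positive C-SSRS form collected in the study, each flagged with days since last dose. This makes late forms visible however the period is defined.
2. Add a C-SSRS exception to SAP 7.4.1. The Premature Discontinuation Visit form should count in Treatment Period C-SSRS summaries when it is completed within 30 days of the last dose and its recall includes on-drug days. The 30-day cap should be mandatory, matching the treatment-emergent adverse event window. Without it, a single on-drug day in the recall could admit a form completed many weeks after stopping.

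The cost is a few lines of SAP text and a small programming change, using forms already collected; nothing changes for subjects or sites. The downside is small: some included forms will also cover off-drug days, and the flag shows when the form was completed, not when the ideation occurred.
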